## LIST OF ABBREVIATIONS

ACC	Adrenocortical Carcinoma
AE	Adverse Event
ALT	Alanine Aminotransferase
ALC	Absolute Lymphocyte Count
AST	Aspartate Aminotransferase
BUN	Blood Urea Nitrogen
CBC	Complete Blood Count
CMP	Comprehensive Metabolic Panel
CR	Complete Response
CT	Computed Tomography
CTCAE	Common Terminology Criteria for Adverse Events
DLT	Dose Limiting Toxicity
DMC	Data Monitoring Committee
DSMB	Data and Safety Monitoring Board
ECOG	Eastern Cooperative Oncology Group
H&PE	History & Physical Exam
IV (or iv)	Intravenously
MTD	Maximum Tolerated Dose
NSCLC	Non-small cell lung cancer
NCI	National Cancer Institute
ORR	Overall Response Rate or Objective Response Rate
OS	Overall Survival
PBMCs	Peripheral Blood Mononuclear Cells
PD	Progressive Disease
PFS	Progression Free Survival
PI	Principal Investigator
PO (or p.o.)	Per os/by mouth/orally
PR	Partial Response
SAE	Serious Adverse Event
RCC	Renal cell carcinoma
SD	Stable Disease
SGOT	Serum Glutamic Oxaloacetic Transaminase
SPGT	Serum Glutamic Pyruvic Transaminase
WBC	White Blood Cells

## STUDY SCHEMA

## STUDY SUMMARY

Title	Phase II study of nivolumab (anti-PD-1 antibody) for treatment of metastatic adrenocortical carcinoma
Short Title	Nivolumab for treatment of metastatic adrenocortical carcinoma
Version	July 5 th , 2016
Study Design	Simon two stage optimum Phase II clinical trial
Study Center(s)	Northwestern Medicine Developmental Therapeutics Institute Robert H. Lurie Comprehensive Cancer Center
Objectives	
Primary: To assess efficacy of nivolumab monotherapy according to objective response rate (ORR) as assessed by RECIST 1.1 in patients with advanced adrenocortical carcinoma
 
Secondary: To assess the efficacy of nivolumab according to progression-free survival (PFS), overall survival (OS)

Sample Size	33 study participants
Diagnosis & Key Eligibility Criteria	Patients with metastatic or locally advanced adrenocortical carcinoma with disease progression after treatment with at least one line of therapy including mitotane and/or chemotherapy.
Treatment Plan	Patients will be treated with nivolumab 240mg as in intravenous infusion over 30 minutes every 2 weeks until confirmed disease progression, unacceptable toxicity, or withdrawal of consent.
Statistical Methodology	Up to 33 patients will enroll in the two stage phase II clinical trial. In the first stage, up to 12 patients will be entered to achieve 10 evaluable. If no patients show a response, then the trial will be terminated due to inactivity of the treatment. If 1 or more of 10 show a response, then up to an additional 21 patients will be added to achieve 19 evaluable. If 3 or fewer of 29 show a response, then the trial will conclude that the response rate could be as low as 5%. If 4 or more respond, then the trial will conclude that the response rate is at least 20%. This design has a 20% chance of falsely concluding the rate is 5% (false negative Type II error rate = 20%, or power = 80%), and a 5% chance of falsely concluding that the rate is 20% (false positive Type I error rate = 5%). Taking into account dropout and patients not evaluable, target accrual will be up to 33 patients.

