## **10.0 STATISTICAL CONSIDERATIONS**

### **10.1 Study Design/Study Endpoints**

A Simon two-stage optimum Phase II design will be used. Up to 33 patients will be entered into the trial. In the first stage, up to 12 patients will be entered to achieve 10 evaluable. If no patients show a response, then the trial will be terminated due to inactivity of the treatment. If 1 or more of 10 show a response, then up to an additional 22 patients will be added to achieve 19 evaluable. If 3 or fewer of 29 show a response, then the trial will conclude that the response rate could be as low as 5%. If 4 or more respond, then the trial will conclude that the response rate is greater than 5%. This design has a 20% chance of falsely concluding the rate is 5% (false negative Type II error rate = 20%, or power = 80%), and a 5% chance of falsely concluding that the rate is 20% (false positive Type I error rate = 5%). There is a 60% probability of early termination of the trial when the true response rate is 5%. Due to inevaluable patients and dropout, target accrual will be up to 33 patients. It is anticipated that 8 patients will be accrued per year so that accrual to this study will take 4 years.

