5.0 (Study Procedures Table)	
 
Listed visits by weeks (“every 2 weeks” and a column for scans “every 8 weeks”) with a <math>\pm</math> 2 day window for visits and <math>\pm</math> 7 days for scans
 
Unclear if physical exam should take place at every treatment visit
 
#7: “A correlative blood sample will be drawn at baseline and after 2 doses of nivolumab”
 
#9: n/a
 
	
 
Changes visits to cycles where 1 cycle = 28 days, and visits have a <math>\pm</math> 3 day window. Scans take place every 2 cycles (rather than 8 weeks) for consistency, and the window has been changed to -7 days
 
Physical exam is only required at Day 1 of each cycle
 
#7: “A correlative blood sample will be drawn pre-dose at C1D1 and C2D15”
 
#9: Study procedures can take place within 24 hours of planned study treatment
 
	
 
Clarification to simplify table; longer visit window accounts more inclusively for unexpected dose delays. +7-day scan window has been removed so that scans take place before dosing
 
Clarification #7: Clarification
 
#9: To allow flexibility if a patient comes from out of town
 

7.7.2 (Expedited Reporting to the NU QAM/DMC; 7.7.4 (Reporting to BMS)	
 
7.7.4 stated “SAE reports will be reported within 24 hours to BMS Global Safety (using the NU CRO SAE Form)”
 
Email was listed incorrectly: [contact];
 
	
 
Added language: “All SAE reports (including death by any cause), regardless of attribution, will be reported within 24 hours to BMS Global Safety (using the NU CRO SAE Form and referencing the BMS study number, CA 209-612).”
 
7.7.2 references BMS reporting instructions in 7.7.4
 
Corrects email typo: [contact]
 
	
 
Clarification for SAE reporting to avoid oversight or deviations
 
Administrative update with correct email
 

10.1 (Study Design / Study Endpoints)	Statistical conclusion stated that “If 4 or more respond then the trial will conclude that the response rate is at least 20%.”	Changes conclusion to: “If 4 or more response then the trial will conclude that the response rate is greater than 5%”	Correction for statistical accuracy

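### The Study Summary reads 4 or more responses in 29 as proof of a rate of at least 20%; Section 10.1 claims only a rate above 5%, which is all the rule supports.

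*Combined protocol and SAP*

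**What the plan says.** Section 10.1 sets the design: "A Simon two-stage optimum Phase II design will be used". Stage sizes are given in evaluable patients: "In the first stage, up to 12 patients will be entered to achieve 10 evaluable", then 19 more, for 29 in total. No responses among the first 10 stops the trial. The Summary's Statistical Methodology row gives the same cutoffs and evaluable numbers.

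The two places share the negative conclusion, which the Summary gives as "If 3 or fewer of 29 show a response, then the trial will conclude that the response rate could be as low as 5" percent. They part on the positive one:

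- Study Summary: "If 4 or more respond, then the trial will conclude that the response rate is at least 20" percent.
- Section 10.1: "If 4 or more respond, then the trial will conclude that the response rate is greater than 5" percent.

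Both state 80% power and describe the type I error as "a 5% chance of falsely concluding that the rate is 20% (false positive Type I error rate = 5" percent. Section 10.1 adds: "There is a 60% probability of early termination of the trial when the true response rate is 5" percent. Section 10.2 plans the response rate with an exact binomial 95% confidence interval.

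**The concern.** One rule on one primary endpoint cannot carry two different conclusions. A rate above 5% and a rate of at least 20% are very different claims in this disease: the protocol's background section puts chemotherapy response rates at 10–20% and mitotane at 10–30%. A reader who relies on the Summary would take a positive trial to show activity at or above the top of that chemotherapy range, when the rule shows only that the rate exceeds 5%.

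The Summary's wording treats the alternative rate used for power as if it were the rate being tested. If followed, it would have the trial declare a rate of at least 20% when the observed rate can be as low as 13.8%.

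**Working it through.** **Inputs** (Study Summary and Section 10.1): n1 = 10 evaluable, stop if 0 responses; n2 = 19, total 29; positive if 4 or more of 29; rates of interest 5% and 20%.

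**Formula.** With X1 ~ Bin(10, p) and X2 ~ Bin(19, p) independent,

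P(positive | p) = Σ over x = 1,…,10 of P(X1 = x) × P(X2 ≥ 4 − x), and P(stop early | p) = (1 − p)^10.

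**Step 1: reproduce the plan's figures.**

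Early stop at 5%: 0.95^10 = 0.5987, the stated 60%.

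| Stage 1 responses | p = 5% | p = 20% |
|---|---|---|
| 1 | 0.31512 × 0.06655 = 0.02097 | 0.26844 × 0.76311 = 0.20485 |
| 2 | 0.07463 × 0.24529 = 0.01831 | 0.30199 × 0.91713 = 0.27697 |
| 3 | 0.01048 × 0.62265 = 0.00652 | 0.20133 × 0.98559 = 0.19843 |
| 4 or more | 0.00103 | 0.12087 |
| **P(positive)** | **0.0468** | **0.8011** |

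The stated 5% type I error and 80% power are therefore correct for a test of 5% with power set at 20%. A search over two-stage designs with type I error at most 5% and power at least 80% also returns 0/10, 3/29 as the optimal design, with an expected sample size of 17.6 at a true rate of 5%.

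**Step 2: how often the rule is positive below 20%.** The same formula gives 0.2889 at p = 10% and 0.5891 at p = 15%. Just below 20% (p = 0.1999) it gives 0.8008. Read as a test of at least 20%, the rule would be wrong about 80% of the time at the edge of its null.

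**Step 3: what a claim of at least 20% would need.** Keep the stage 1 rule and raise the final cutoff. At p = 20% the chance of a positive result is 0.1077 with 9 or more responses and 0.0491 with 10 or more. A one-sided 5% claim therefore needs 10 of 29, not 4.

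**Step 4: observed rates at the cutoff.** 4/29 = 13.8%, 5/29 = 17.2%, 6/29 = 20.7%. Exact (Clopper–Pearson) 95% intervals are 3.9% to 31.7% for 4/29 and 5.8% to 35.8% for 5/29.

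**Step 5: how often a positive trial has an observed rate below 20%** (4 or 5 responses in total, having passed stage 1):

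| True rate | P(4 or 5, positive) | P(positive) | Share of positive trials |
|---|---|---|---|
| 10% | 0.2281 | 0.2889 | 79% |
| 15% | 0.3376 | 0.5891 | 57% |
| 20% | 0.2820 | 0.8011 | 35% |

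**Step 6: the plan's other wording.** The shared negative conclusion and the early-termination figure both take 5% as the rate being tested, in line with the positive conclusion in Section 10.1 and not with the Summary's.

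**The case against.** The strongest reply is that this is one unsynchronised phrase in a synopsis. Section 10.1 states the supported conclusion, Section 10.2 requires an exact interval, and no patient, cutoff or reported estimate changes. That is true and limits the consequence. It does not remove the point, because the sentence states the trial's conclusion on its primary endpoint and no text says which section prevails. The case for Section 10.1 therefore rests on the arithmetic.

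Three further qualifications stand:

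- An observed 13.8% or 17.2% does not refute a true rate of 20%, since both exact intervals include 20%. The fault is that at least 20% is not established.
- A rate above 5% is supported as a one-sided test at about the 5% level. The plan does not state sidedness; it follows from the form of the rule. At exactly 4/29 the planned two-sided 95% interval starts at 3.9% and so still includes 5%.
- The 79% and 57% shares assume true rates of 10% and 15%, which are not design points. At the design alternative of 20% the share is 35%.

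It can also be said that Section 10.1 is not wholly clean, since both places describe the type I error as falsely concluding that the rate is 20%. The figure of 5% is right at a true rate of 5%; the description is loose and is worth aligning in the same edit.

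**Conclusion.** The concern holds. Two current statements of the same rule give different primary conclusions, and the Summary's is not supported. The rule limits a false positive to 4.7% at a true rate of 5%, but it is positive with probability 28.9% at 10% and 58.9% at 15%. A positive result therefore cannot be read as a rate of at least 20%.

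The figures assume exactly 10 and 29 evaluable patients, independent responses with a common rate, and the rule applied as written.

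The likely origin is a partly applied correction. The Summary's version date, July 5, 2016, is that of Amendment 2, for which Appendix E records the change to this sentence in Section 10.1 as "Correction for statistical accuracy". The contradiction stands without that history. It should be fixed, though its practical effect is small.

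**What to change.** In the Study Summary's Statistical Methodology row, replace the conclusion of a rate of at least 20% with the Section 10.1 conclusion of a rate greater than 5%.

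Optionally, in the same edit, reword the type I error in both places as a 5% chance of concluding that the rate exceeds 5% when the true rate is 5%.

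The cost is one phrase in the Summary and, if the option is taken, one clause in each place. Sample size, cutoffs, data collection and analyses stay as they are.

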## 1.0 INTRODUCTION – BACKGROUND & RATIONALE

### 1.1 Disease Background

Adrenocortical carcinoma (ACC) is an exceedingly rare malignancy with no effective standard treatment options. ACC is responsible for 0.2% of all cancer deaths in the United States and has an estimated incidence of 0.7 cases per million per year [1, 2]. The disease incidence has a bimodal distribution with peaks in first and fourth decades with a female to male ratio 1.5-2.5:1 [3, 4]. While a growing number of patients are diagnosed with early stage and indolent disease incidentally after having abdominal CT scans, the majority of patients (40-60%) present with symptoms related to excessive hormonal production (i.e. hypercortisolism or hyperandrogenism)[3, 5]. Surgery is the treatment of choice for patients presenting with localized disease and is often followed by adjuvant chemotherapy with mitotane to mitigate the risk of disease recurrence in high-risk patients [6-8]. The group of approximately 30-70% of patients presenting with metastatic disease carry an extremely poor prognosis related to the aggressive biological behavior and lack of effective therapeutic options [3, 5]. The 5-year survival rate for this patient population is estimated at less than 15% [9].

Mitotane, the only FDA-approved drug for ACC, displays single-agent activity (10-30% tumor response rates) based on its adrenolytic activity but its broad clinical use is challenged by an unfavorable toxicity profile [10-12]. Chemotherapy has also limited efficacy in advanced disease with retrospective studies showing response rates of 10-20% [13-15]. The only phase 3 randomized clinical trial ever conducted in advanced ACC showed that mitotane combined with etoposide, doxorubicin and cisplatin (EDPM) provided additional clinical benefit compared to mitotane plus streptozocin [16]. In spite of higher tumor response rates with EDPM (23% vs. 9%) and prolongation of progression-free survival (PFS; 5 vs. 2 months), there was no significant benefit in median overall survival (OS; 14 vs. 12 months) and up to 58% of patients receiving EDPM had serious adverse events. In fact, as a clear statement to the unmet need for effective treatments, the National Comprehensive Cancer Network recommendations for first line treatment of metastatic ACC include consideration of systemic therapies in clinical trials.

Advances in the molecular understanding of pathogenesis revealed novel therapeutics targets but no definitive efficacy with targeted therapies have been demonstrated. The role of the insulin growth factor (IGF) pathway in adrenal gland development coupled with results showing that overexpression of IGF2 in 80% of ACC tumors correlates with worse outcome provided the rationale for investigating inhibitors of the IGF-1R [17-20]. Nevertheless, a placebo-controlled phase III trial evaluating the IGF1-R inhibitor linsitinib among 139 patients with recurrent or metastatic ACC following first or second line treatments showed no improvement in PFS or OS (10.8 vs. 11.8 months) [21]. Disappointing results were also seen with agents blocking the VEGF pathway including bevacizumab, sorafenib, and sunitinib despite preclinical data supporting angiogenesis as a relevant therapeutic target [6, 22-24]. Even though results of comprehensive genetic profiling revealed promising therapeutic targets, strategies beyond interfering with disrupted cancer cell signaling are urgently needed [25]. Hence, immunotherapy approaches emerge as potential treatment options clinically feasible with novel checkpoint inhibitors. We propose to investigate the safety and efficacy of the monoclonal antibody against programmed death-1 (PD-1) nivolumab for the treatment of metastatic ACC.

## 1.2 Intervention Overview & Background

### 1.2.1 Overview

Nivolumab (BMS-936558, MDX-1106) is a fully human monoclonal immunoglobulin G4 (IgG4) antibody (HunMab) that is specific for human programmed death-1 (PD-1, cluster of differentiation 279 [cd279]) cell surface membrane receptor (Investigator Brochure version 2014). PD-1 is a negative regulatory molecule that is expressed transiently following T-cell activation and on chronically stimulated T cells characterized by an “exhausted” phenotype. Nivolumab anti-tumor activity has been investigated in patients with melanoma, non-small cell lung cancer (NSCLC), and renal cell carcinoma (RCC). The combination of nivolumab and ipilimumab (anticytotoxic T lymphocyte associated antigen-4 [anti-CTLA-4]) in phase 1/2 trial showed markedly enhanced clinical activity with acceptable safety profile in melanoma patients [26].

The clinical use of monoclonal antibodies to T-cell inhibitory receptors has provided transformative information on the nature of the immune system and cancer. An emerging picture suggests that endogenous immune responses can mediate effective tumor regression and/or improved survival even in patients with large volume tumors resistant to other forms of therapy. Some of the unique features of this type of therapy, based largely on experience in advanced melanoma, include: improved overall survival (OS) with or without radiographic responses or improved progression-free survival (PFS); responses that may be delayed or occur after radiographic disease progression; combinations of immune modulators with enhanced or novel activities (in the example of ipilimumab and nivolumab); and toxicity that is almost exclusively immune or inflammatory in nature. It is not yet clear what factors determine responses and which components of the immune system are needed for this to occur. It seems likely that both memory helper and effector cells would be needed to sustain long-term responses. Increasing emphasis has been placed on understanding the relationships of the tumor, cellular infiltrate, and immunologic milieu surrounding each tumor.

PD-1, a 55-kDa type 1 transmembrane protein, is a member of the CD28 family of T-cell co-stimulatory receptors that include Ig super family member CD28, CTLA-4, inducible co-stimulator (ICOS), and B and T lymphocyte attenuator (BTLA) (Investigator Brochure version 2014). PD-1 is transiently but highly expressed on activated T cells functioning to limit immune effectors at the site of activation. Chronic stimulation may prevent the re-methylation of the PD-1 gene leading to continuous expression and characterizes a state of “exhausted” T cells that lose function and proliferative capacity while enhancing a suppressive tumor microenvironment. PD-1 may act together with other T-cell modulating molecules, including CTLA-4, TIM-3, lymphocyte-activation gene 3 (LAG-3) as well as indoleamine-pyrrole 2, 3-dioxygenase 1 (IDO-1), cytokines, and transforming growth factor beta (TGF-beta).

Two ligands specific for PD-1 have been identified: PD-ligand 1 (PD-L1, also known as B7-H1 or CD274, expressed on tumor, antigen-presenting cells [APCs], and dendritic cells [DCs]) and PD-L2 (also known as B7-DC or CD273, expressed on endothelial cells). The interaction of PD-1 with PD-L1 and PD-L2 results in negative regulatory stimuli that down-

modulate the activated T-cell immune response through SHP-1 phosphatase.

PD-1 knockout mice develop strain-specific lupus-like glomerulonephritis (C57BL/6) and cardiomyopathy (BALB/c). In transplantable tumor models that expressed PD-1 and LAG-3 on tumor-infiltrating CD4+ and CD8+ T cells dual anti-LAG-3/anti-PD-1 antibody treatment cured most mice of established tumors that were largely resistant to single antibody treatment [27]. Despite minimal immunopathologic sequelae in PD-1 and LAG-3 single knockout mice, dual knockout mice abrogated self-tolerance with resultant autoimmune infiltrates in multiple organs, leading to eventual lethality.

PD-L1 expression is found on a number of tumors, and is associated with poor prognoses based on OS in many tumors, including melanoma, renal, esophageal, gastric, ovarian, pancreatic, lung, and other cancers (Investigator Brochure version 2014) [28-34]. No published data is available evaluating PD-L1 expression in adrenocortical carcinoma.

### **1.2.2 Clinical development of nivolumab**

Nivolumab is being evaluated as monotherapy and in combination with cytotoxic chemotherapy, other immunotherapy (such as ipilimumab), anti-angiogenesis therapy, and targeted therapies in completed and ongoing BMS-sponsored clinical trials in NSCLC, melanoma, RCC, hepatocellular carcinoma (HCC), gastrointestinal (GI) malignancies including colorectal cancer with microsatellite instability (MSI), and triple-negative breast cancer (TNBC) with an expanding group of indications (Investigator Brochure version 2014). Nivolumab is currently FDA approved for the treatment of patients with: (i) unresectable or metastatic melanoma and disease progression after ipilimumab and, if BRAF V600 mutation positive, a BRAF inhibitor; (ii) patients with metastatic squamous non-small cell lung cancer with progression on or after platinum-based chemotherapy.

### **1.2.3 Clinical efficacy**

Nivolumab has demonstrated clinical activity as monotherapy and as combination therapy with ipilimumab in several tumor types, including RCC, melanoma, NSCLC, and some lymphomas. The majority of responses was durable and exceeded 6 months (Investigator Brochure version 2014). Nivolumab is being investigated both as monotherapy and in combination with chemotherapy, targeted therapies, and other immunotherapies.

In a phase 1 (1, 3, and 10 mg/kg nivolumab doses) dose-escalation study the 3 mg/kg dose was chosen for expanded cohorts. Among 236 patients, objective responses (ORs) (complete or partial responses [CR or PR]) were seen in NSCLC, melanoma, and RCC. ORs were observed at all doses. Median OS was 16.8 months across doses and 20.3 months at the 3 mg/kg dose. Heavily pretreated patients with NSCLC treated with nivolumab (1, 3, or 10mg/kg) achieved median OS across all dose cohorts of 9.9 months with response rates of 17% and median duration of response 17 months [35]. In addition, responses were similar between both squamous and non-squamous carcinoma cohorts in this study. A subsequent phase 3 study compared nivolumab to docetaxel in second-line treatment setting of advanced squamous cell carcinoma among 272

patients. Nivolumab arm demonstrated superior median OS (9 vs 6 months), 1 year survival rate (42 vs 24%), response rates (20 vs 9%), and significantly lower rates of grade 3-4 treatment related adverse events (7 vs 55%) [36]. These results supported the FDA approval of nivolumab for second-line treatment of advanced squamous cell carcinoma following treatment with platinum-based chemotherapy.

Nivolumab has also clinically meaningful activity in RCC. A phase II study treated 168 patients with advanced clear cell RCC with progression after agents targeting VEGF pathway at three doses of nivolumab (0.3, 2 and 10mg/kg) [37]. Median overall survival was 18, 25, and 24 months for the three dose cohorts, respectively. Response rates were in average 20% with only 11% incidence of grade 3-4 treatment-related adverse events. In an advanced melanoma phase 1 study, nivolumab and ipilimumab were administered IV every 3 weeks for 4 doses followed by nivolumab alone every 3 weeks for 4 doses (concurrent regimen) [26]. The combined treatment was subsequently administered every 12 weeks for up to 8 doses. In a sequenced regimen, patients previously treated with ipilimumab received nivolumab every 2 weeks for up to 48 doses. In the concurrent regimen (53 patients), 53% of patients had an OR at doses 1 mg/kg nivolumab and 3 mg/kg ipilimumab, with tumor reduction of 80% or more (modified World Health Organization criteria). In the sequenced-regimen (33 patients), the objective response rate (ORR) was 20%. These results demonstrate significant clinical activity of nivolumab across multiple histologies with favorable toxicity profile.

